18.3.2. Pregnancy Tests

Urine beta-human chorionic gonadotropin (β -hCG) and/or serum β -hCG pregnancy tests are performed throughout the study in female subjects of childbearing potential. All pregnancy test results (positive or negative) will be listed in chronological order.

18.3.3. Other Screening Laboratory Assessments

Screening laboratory assessments for virology, drug screen/toxicology, QuantiFERON Tuberculosis (TB) Gold, stool pathogens, and *Clostridioides difficile* (formerly known as *Clostridium difficile*) will be listed. Analyses of genetics [REDACTED] data based on samples collected at Screening in subjects who provided consent will be described in a separate plan.

18.4. ECG Evaluations

ECGs are recorded on a 12-lead ECG machine and read centrally. The following ECG parameters are reported for this study:

- HR (bpm)
- PR interval (ms)
- RR interval (ms)
- QRS interval (ms)
- QT interval (ms)
- QTcF interval (ms)
- Overall interpretation of ECG (Investigator's judgment):
 - Normal
 - Abnormal, Not Clinically Significant (Abnormal NCS)
 - Abnormal, Clinically Significant (Abnormal CS)

- Overall interpretation of ECG (central reader):
 - Normal
 - Abnormal NCS
 - Abnormal CS
- AV conduction abnormalities
 - First-degree AV block
 - Second-degree AV block type 1
 - Second-degree AV block type 2
 - Third-degree AV block

The following summaries will be provided for ECG data:

- Value and change from Baseline by visit (for quantitative measurements)
- Incidence of markedly abnormal values (defined in Section 18.4.1) and AV blocks by visit
- Shift in normal/abnormal NCS/abnormal CS in the overall interpretation (by investigator) from Baseline to end of treatment and to the worst-case post-Baseline
- Shift in markedly abnormal categories from Baseline to post-Baseline by visit

Listings of ECG results, including first dose cardiac monitoring, and discharge criteria for first dose cardiac monitoring will be provided.

A listing of all ECG assessments over time in subjects meeting markedly abnormal criteria will also be provided. For each subject, only ECG parameters ever meeting markedly abnormal criteria will be included.

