1.3. Benefit/Risk Assessment

Considering the significant unmet need for safe and effective, orally administered treatments for UC, etrasimod may potentially provide therapeutic benefit via S1P receptor modulation.

Adverse events that have been reported with S1P receptor modulators include bradycardia at the first dose or atrioventricular (AV) block, macular edema, hypertension, headache, cough, dyspnea, back pain, influenza, and diarrhea.

Safety and tolerability of etrasimod has been evaluated in Phase 1 studies with healthy adult subjects at single doses up to 5 mg and repeated doses up to 4 mg once daily. Repeated doses of 2 mg have been evaluated in Phase 2 studies of subjects with moderately to severely active UC (refer to the current edition of the IB). Etrasimod was found to be safe and well tolerated in these studies, with no clinically significant safety concerns with respect to vital signs, electrocardiograms (ECGs), pulmonary function tests (PFTs), ophthalmoscopy, or clinical laboratory tests. Etrasimod produced a dose-dependent sustained decrease in total lymphocyte count, which is expected given etrasimod's mechanism of action. Lymphocyte counts were within normal limits by 7 days after the last dose.

Detailed information regarding the known and expected benefits and risks and reasonably expected adverse events of etrasimod can be found in the IB.

Based on the mechanism of action of etrasimod and prior experience with other agents acting via a similar mechanism, monitoring for specific safety parameters are planned for this study, which include: auscultation of the lungs as part of the physical exam; PFT, exclusion of subjects with macular edema or retinopathy, with assessment of optical coherence tomography (OCT) occurring throughout the study; and exclusion of subjects with certain cardiac risks, with assessment of vital signs in the period following dosing.

- Auscultation of lungs will be conducted as part of the physical examination.
- Prospective subjects with a history of macular edema or retinopathy will be excluded from the study. All randomized subjects will be assessed by OCT at study entry, periodically throughout the treatment period, and as clinically indicated any time during the study.

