9.10.2. Vital Signs

Resting vital signs measurements will be performed according to the Schedules of Assessments (Table 7 and Table 8) with the subject in the sitting position. Vital signs will be measured prior to any blood draws that occur at the same study visit.

Blood pressure may be measured manually or by automated device. Proper technique should be utilized during the measurement of BP to include the following:

- The subject's arm should be bare and supported at heart level.
- An appropriately sized cuff (cuff bladder encircling at least 80% of the arm) should be utilized. Subject's legs should not be crossed during the evaluation.

9.10.3. 12-Lead Electrocardiogram

All 12-lead ECGs will be performed according to Section 9.4.2.1 and the Schedules of Assessments (Table 7 and Table 8), and if clinically indicated at any time during the treatment period per Investigator discretion. All ECGs will be recorded from a 12-lead ECG machine with the subject in the supine position. Every attempt should be made to ensure the subject 12-lead ECG readings are obtained using the same machine throughout the study.

Intervals to be provided on the confirmed read for each safety 12-lead ECG are: RR, PR, QRS, QT, and QTcF. If an ECG shows a new onset QTc interval > 500 ms during the treatment period, a repeated ECG is warranted. If this abnormal finding is confirmed, study treatment must be interrupted. Effective diagnostic and therapeutic strategies should be employed.

Reversible causes of prolonged QTc interval (eg, electrolyte abnormalities or hypomagnesemia), should be corrected as clinically indicated. When evaluating a subject with new onset QTc interval above 500 ms, referral to a cardiologist experienced in treating cardiac conduction disorders should be considered. Re-initiation of study treatment can only be considered after all of the following have occurred:

- The QTcF interval is < 450 ms (men) or < 470 ms (women)
- The QTc prolongation is considered by the Investigator and confirmed by the cardiologist as not related to study treatment and likely caused by other factors
- Individual risk-benefit is favorable (as determined by the Investigator, in agreement with the cardiologist), **AND**
- After discussion with the Medical Monitor.

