6.4. Windowing Conventions

All scheduled study visits are defined relative to Study Day 1, the date of first dose. Scheduled visit windows are defined in Clinical Study Protocol APD334-301 Appendix 1. A windowing convention will be used to determine the analysis visit value for a given measurement and will be applicable for all by-visit summaries and analyses for efficacy and safety data. Refer to [Table 2](#) for specific visit windows.

Table 2: Visit Windows for Efficacy and Safety Analyses

For all efficacy (except endoscopy/MMS/histology), efficacy-related biomarkers, safety labs and vital signs	
Scheduled Study Visit (Protocol Scheduled Day)	Analysis Visit Window (Study Day)
Baseline	≤ 1
Week 0 (Day 1)	1
Week 0 (Day 2) ^a	2
Week 2 (Day 15 ± 3)	2 to 22, or 3 to 22 ^a
Week 4 (Day 29 ± 3)	23 to 43
Week 8 (Day 57 ± 3)	44 to 71
Week 12 (Day 85 ± 7)	72 to 99
Week 16 (Day 113 ± 7)	100 to 127
Week 20 (Day 141 ± 7)	128 to 155
Week 24 (Day 169 ± 7)	156 to 197
Week 32 (Day 225 ± 7)	198 to 253
Week 40 (Day 281 ± 7)	254 to 309
Week 48 (Day 337 ± 7)	310 to 351
Week 52 (Day 365 ± 14)	> 351
For endoscopy/MMS/histology/all composite endpoints that include an endoscopy component and/or RB/SF component, Physician’s Global Assessment, health-related quality of life, ECGs, OCT, and PFT	
Scheduled Study Visit (Protocol Scheduled Day)	Analysis Visit Window (Study Day)
Baseline	≤ 1
Week 0 (Day 1)	1
Week 0 (Day 2) ^a	2
Week 12 (Day 85 ± 7) ^{b,c}	66 to 113 (66 to 141 for assessments impacted by COVID-19 pandemic) ^d
Week 32 (Day 225 ± 7) [PFT only]	198 to 253 (198 to 281 for assessments impacted by COVID-19 pandemic) ^d
Week 52 (Day 365 ± 14) ^{b,d}	337 to 393 (337 to 421 for assessments impacted by COVID-19 pandemic) ^e

^a Applicable only for subjects who require extended monitoring on Day 2 for vital signs and ECGs.

^b Applicable to all Week 12 and Week 52 efficacy endpoints based on any component of Mayo clinic score, such as clinical remission and symptomatic remission. Protocol visit window for PFT and OCT at Week 12 is Day 85 ± 7 (FDA 2020).

^c Due to overlapping windows at Week 12 and Week 8/16, a hierarchical algorithm will be used for the mapping. Week 12 will always be mapped first, then assess records for the Week 8/16 mapping. If a scheduled Week 8 and 12, or Week 12 and 16 visits are both present in the same visit window, they will be mapped to separate visits (ie, Week 8 and Week 12 or Week 12 and Week 16).

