^d Due to overlapping windows in the RB/SF components at Week 52 and Week 48, a hierarchical algorithm will be used for the mapping. Week 52 will always be mapped first, then assess records for the Week 48 mapping. If a scheduled Week 48 and 52 visits are both present in the same visit window, they will be mapped to separate visits (ie, Week 48 and Week 52).

^e Assessments impacted by the COVID 19 pandemic are reported in the Date of Visit eCRF.

COVID-19, coronavirus disease 2019; ECG, electrocardiogram; eCRF, electronic case report form; MMS, modified Mayo Score; OCT, optical coherence tomography; PFT, pulmonary function test; RB, rectal bleeding; SF, stool frequency.

For cardiac remonitoring upon treatment reinitiation after Day 2, as manifested by more than 1 timed measurement in vital signs or electrocardiogram (ECG) parameters on the same collection date of an unscheduled visit, measurements will be mapped to analysis visit of Cardiac Remonitoring 1, Cardiac Remonitoring 2, etc. in the respective analysis dataset. For analysis, each timed measurement will be programmatically assigned to the nearest hourly timepoint (eg, Predose, 1-hour Postdose) based on their relationship to the dosing time on the same day. If the dosing date/time on the same day is missing, the timepoint will remain missing. Once mapped, these timed measurements from cardiac remonitoring visits will not be considered for any other analysis visit.

Windowing will be applied prior to any missing data calculations. The last nonmissing measurement taken prior to Day 1 (including unscheduled assessments) will be labeled as “Baseline”. Unless stated otherwise, data from all visits including scheduled, unscheduled, and ET visits will be eligible for allocation to an analysis visit. The 2-Week and 4-Week Follow-Up visits will not be included in the visit windows and will be summarized separately without any window applied.

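### The SAP's 500 ms ECG criterion uses uncorrected QT, and ECG and combined liver thresholds are counted only by visit, so many off-window ECGs have no row to be counted in

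*SAP*

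**What the plan says.** **ECG thresholds.** SAP 18.4.1 lists QTcF ≥ 450 ms (men) or ≥ 470 ms (women), QT > 500 ms, and increases of more than 30 and 60 ms. SAP 18.4 tabulates these in two ways: "Incidence of markedly abnormal values (defined in Section 18.4.1) and AV blocks by visit" and "Shift in markedly abnormal categories from Baseline to post-Baseline by visit". The one worst-case ECG summary, "from Baseline to end of treatment and to the worst-case post-Baseline", is for the investigator's overall interpretation and not for intervals.

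**Protocol threshold.** Protocol 9.10.3 uses the corrected interval: "If an ECG shows a new onset QTc interval > 500 ms during the treatment period", the ECG is repeated, with further action if the finding is confirmed. Protocol 1.3 names "bradycardia at the first dose or atrioventricular (AV) block" among events reported with this drug class.

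**Which ECGs exist.** Protocol Tables 7 and 8 schedule an ECG at Early Termination. Protocol 9.10.3 also allows ECGs "if clinically indicated at any time during the treatment period per Investigator discretion".

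**Where they are counted.** SAP 6.3 assigns by-visit data to visits after windowing, and also says that every measurement counts in summaries of abnormalities. SAP 6.4 says that "data from all visits including scheduled, unscheduled, and ET visits will be eligible for allocation to an analysis visit". The second block of Table 2, which covers "health-related quality of life, ECGs, OCT, and PFT", gives ECGs only Day 1, Day 2, Days 66-113 and Days 337-393; its Week 32 row is for PFT alone. When several values fall in one window, 6.4 generally uses the one closest to the scheduled day.

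**Liver.** SAP 18.3.1 counts hepatic elevations, including ALT/AST > 3x with total bilirubin > 2x ULN, by visit. For lymphocytes and neutrophils the same section adds an any-time count. The eDISH plots pair each subject's maximum enzyme value with bilirubin from the same day.

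**The concern.** A safety threshold table should answer two questions: how many subjects per arm ever crossed a limit that matters, and whether that limit is measured in a way that does not shift with heart rate.

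The 500 ms row does not meet the second need. At one and the same corrected interval, uncorrected QT is longer when the heart is slower. If the arms differ in heart rate, the row can differ between them for that reason alone. The protocol's own action threshold, QTc > 500 ms, is never tabulated.

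The by-visit layout does not meet the first need. ECGs taken because a subject stopped early, or because an investigator saw a reason, are among the most informative, and they can fall on days that belong to no analysis visit. For the liver criteria, by-visit rows do not give the number of subjects who ever met them.

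**Working it through.** **1. QT against QTcF.** QTcF = QT × (HR/60)^(1/3). The heart rates are chosen for illustration.

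- 60 bpm: the two are equal.
- 75 bpm: QT 500 ms gives QTcF 500 × 1.0772 = 538.6 ms. A QTcF of 501 to 538 ms therefore enters no 500 ms row.
- 50 bpm: QT 501 ms gives QTcF 501 × 0.9410 = 471.5 ms, and QTcF 500 ms needs QT 531.3 ms. A QT of 501 to 531 ms therefore enters the row with a QTcF of at most 500 ms.

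At a mapped visit a QTcF > 500 ms still enters the 450/470 ms row. Entry required QTcF < 450 ms (men) or < 470 ms (women), so it also enters the > 30 ms row (500 − 470 = 30). There it is counted but not separable.

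**2. Days without an ECG window (SAP Table 2).**

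- Days 3-65: 65 − 3 + 1 = 63.
- Days 114-336: 336 − 114 + 1 = 223.
- Total: 63 + 223 = 286 of Days 1-365.
- For COVID-impacted assessments the Week 12 window runs to Day 141, leaving 286 − 28 = 258.

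Remonitoring ECGs after Day 2 go to their own analysis visits. The same check on the laboratory windows finds no gap from Day 1 onward.

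**3. Early Termination ECGs that could be unmapped.** SAP 16.1.4.1 projects 50% dropout: 0.50 × 420 = 210 at most. The documents give no timing, so the rest is assumption.

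- *Constant dropout rate*, λ = ln 2/365, so the fraction remaining at day t is 2^(−t/365). Dropout on Days 3-65 is 0.9962 − 0.8839 = 0.1123. On Days 114-336 it is 0.8069 − 0.5283 = 0.2786. As a share of all dropout: (0.1123 + 0.2786)/0.50 = 0.782, and 0.782 × 210 ≈ 164. Placing the visit 7 days after dropout gives 162.
- *Clustering at Week 12*, where entry to the extension study opens. Let a share s fall on Days 66-113 and the rest follow the same rate. The constant-rate share for Days 66-113 is (0.8839 − 0.8069)/0.50 = 0.154. The unmapped number is 210 × (1 − s) × 0.782/(1 − 0.154).

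| s | Unmapped Early Termination ECGs |
|---|---|
| 0.25 | 146 |
| 0.50 | 97 |
| 0.75 | 49 |

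These figures count ECGs without a visit, not threshold crossings. The number of crossings cannot be derived.

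**4. Liver rows.** Four visit rows for a single-enzyme threshold, each showing 1 subject, look the same whether one subject was elevated four times or four subjects once each.

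An invented case shows the rule conflict: ALT 6x with bilirubin 1.4x on Day 29, then ALT 4x with bilirubin 2.6x on Day 43. Both days lie in the Week 4 window (Days 23-43, scheduled Day 29).

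- 6.3, all measurements: the combined criterion is met, count 1.
- 6.4, closest value: only Day 29 is used, count 0.
- eDISH: the point plotted is (6, 1.4), outside the > 3x/> 2x quadrant.

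**5. Local bilirubin.** SAP 18.3 keeps local values out of summaries (lipid and thyroid panels excepted) and out of worst values. SAP 18.3.1 ranks central over local bilirubin for the eDISH plot, which presupposes that a local value may be plotted.

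**The case against.** The strongest reply is SAP 6.3: if every measurement counts in summaries of abnormalities, off-window ECGs are covered. A reader might go the other way and infer that the SAP excludes them. Neither reading is secure. The sentence includes them in principle, but both threshold tables are by visit and an ECG on Day 200 has no visit. The SAP does not say where it is counted.

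Several other replies stand, at least in part:

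- **Listings.** All ECGs of subjects meeting a criterion are listed, so the information exists. A per-arm tally could be made by hand, but it is not a planned output.
- **AESI review.** SAP 18.1.5 has ECG and transaminase data reviewed for unreported cases. This helps for bradycardia, AV conduction and liver injury. QT prolongation is not among the listed categories.
- **Liver substitutes.** The combined criterion requires treatment discontinuation under Protocol 5.1, and the SAP counts liver-related events leading to discontinuation. Repeated counting of one subject on that criterion is therefore less likely than for single enzymes. These counts and the eDISH plots are partial substitutes.
- **The 210.** The 50% rate was set to choose the number of imputations. Subjects who withdraw consent or are lost to follow-up may have no Early Termination ECG, so at that rate 210 is a ceiling and the figures derived from it are upper values.

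A reader might also infer that a QTcF > 500 ms would go uncounted everywhere, or that liver tests fall into window gaps too. Neither is so: mapped visits catch the former in other rows, and the laboratory windows are continuous after dosing.

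**Conclusion.** The point holds in a limited form. The 500 ms criterion does not match the protocol's and depends on heart rate. How far the arms' heart rates would differ at Weeks 12 and 52 is not stated, so the size of any resulting imbalance is unknown.

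Outside the stated exceptions, unscheduled and Early Termination ECGs on Days 3-65 and 114-336 have no threshold row. Their interval values appear only in listings. The window gap is exact; the number of ECGs in it is not, and the range of 49 to 164 rests on the dropout rate, on complete Early Termination attendance and on assumed timing. It should not be read as a number of missed signals.

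For the liver, the defect is narrower: there is no any-time subject count per arm, and 6.3 and 6.4 can give different by-visit counts. The local-bilirubin conflict is a minor clarification.

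Listings, adverse event outputs and efficacy analyses are unaffected.

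**What to change.** 1. In SAP 18.4.1, add a QTcF > 500 ms category and leave the 30 and 60 ms criteria as they are.
2. In SAP 18.4, report the 18.4.1 criteria also at any time post-baseline, from all ECGs, including unscheduled and Early Termination.
3. In SAP 18.3.1, add an any-time post-baseline count per arm from all measurements, at least for ALT/AST > 3x with total bilirubin > 2x ULN.
4. State that for abnormality counts 6.3 takes precedence over the closest-value rule in 6.4.
5. Reconcile SAP 18.3 with the eDISH bilirubin sentence in 18.3.1 so that one rule applies. Whether local liver values are used is for the sponsor to decide.

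The cost is SAP wording and a few table rows. No new data are needed.

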18.4.1. ECG Markedly Abnormal Criteria

Markedly abnormal quantitative ECG measurements will be identified in accordance with the following predefined markedly abnormal criteria:

- Absolute values in QT and QTcF:
 - ≥ 450 ms (male) or ≥ 470 ms (female) in QTcF
 - > 500 ms in QT
- Change from Baseline in QT and QTcF:
 - > 30 ms increase from Baseline
 - > 60 ms increase from Baseline

In shift tables, subjects will be classified according to each binary category for each parameter and the predefined markedly abnormal criterion (ie, Markedly abnormal versus Not markedly abnormal, with Markedly abnormal defined in the footnote).

18.5. Vital Signs

The following vital signs measurements are reported for this study:

- Systolic blood pressure (mm Hg)
- Diastolic blood pressure (mm Hg)
- Heart rate (bpm)
- Respiratory rate (resp/min)
- Temperature (°C)
- Weight (kg)
- Height (cm) (Screening only)

The following summaries will be provided for vital signs data:

- Value and change from Baseline by visit
- Value and change from predose on Day 1 (as reported on the eCRF) by timepoint
 - For heart rate only, value and change from predose to minimum postdose heart rate on Day 1 will be included in the same table
- Incidence of markedly abnormal values (defined in [Table 4](#) by visit)
- Listing of subjects meeting markedly abnormal criteria
- Incidence of minimum heart rate on Day 1 by postdose timepoint (1, 2, 3, 4, and > 4 hours postdose, and Day 1 overall) and heart rate interval (≥ 65 , 60 to 64, 55 to 59, 50 to 54, 45 to 49, 40 to 44, < 40 bpm)
 - If minimum heart rate is attained at multiple postdose timepoints, only the earliest timepoint will be counted in this incidence summary
- Time to minimum heart rate on Day 1 by planned hourly timepoint (if minimum heart rate is attained at multiple postdose timepoints, only the earliest timepoint will be counted).
 - Actual time elapsed from first dose to minimum heart rate on Day 1 will also be summarized using descriptive statistics (n, mean, SD, median, minimum, and maximum) in the same table
- Line plots for mean value and mean change from predose on Day 1, up to 4 hours postdose, by parameter and timepoint (systolic blood pressure, diastolic blood pressure, and heart rate)
- Line plots for mean value and mean change from Baseline by parameter and visit (systolic blood pressure, diastolic blood pressure, heart rate, body temperature, and respiratory rate)

Listings of all vital signs, including first dose cardiac monitoring, and discharge criteria for first dose cardiac monitoring will be provided. A listing of vital signs assessments over time in subjects meeting a markedly abnormal criterion will also be provided. For each subject, only the parameters with at least one markedly abnormal criterion satisfied will be included.

For subjects with extended monitoring or remonitoring, a listing of systolic blood pressure, diastolic blood pressure, heart rate values, and change from predose in all parameters on Day 1, Day 2, and any remonitoring visit will be provided.

18.5.1. Vital Signs Specific Derivations

- Temperature (°C) = (5/9) (Temperature (°F) – 32)

18.5.2. Vital Signs Markedly Abnormal Criteria

Markedly abnormal quantitative vital signs measurements will be identified in accordance with the following predefined markedly abnormal criteria:

Table 4: Markedly Abnormal Criteria for Vital Signs

Variable	Unit	Low	High
SBP	mm Hg	≤ 90 mm Hg	> 150 mm Hg
DBP	mm Hg	≤ 50 mm Hg	> 90 mm Hg
Heart rate	bpm	< 40 bpm < 50 bpm < 50 bpm and decrease from predose (Baseline) of > 10 bpm at 4 hours on Day 1 or Day 2 or remonitoring visit	> 100 bpm

bpm, beats per minute; DBP, diastolic blood pressure; SBP, systolic blood pressure

